6.1.1 Tumour Burden

Tumour burden will be assessed using the following statement:

On the basis of initial metastatic disease pattern and if allocated to the SBRT group, would SBRT be performed on all known disease?

If YES – this would represent a low tumour burden

If NO – this would represent a high tumour burden

This information will be requested at randomisation to minimise any bias occurring due to imbalanced distribution of tumour burden between the two groups.

ICR-CTSU

7 SCREENING

7.1 Screening Log

All participating sites will be required to keep a log of all participants with locally assessed radiologically defined oligoprogression upon TKI treatment potentially eligible for this study. The information collected on the log will include:

- Date patient identified
- Number of patients approached/accepting/declining participation/ineligible
- Screening outcome
- Trial ID (if applicable)
- Reasons for ineligibility / not approaching / declining as applicable (if available)

This information will be used to monitor recruitment activity. No patient identifiable data will be sent to ICR-CTSU from the screening log.

7.2 Procedure for Obtaining Informed Consent

The Principal Investigator (or designated individual) must ensure that each trial patient is fully informed about the nature and objectives of the trial and possible risks associated with participation. No protocol required assessments should be conducted until the appropriate consent form has been signed and dated by both the patient and the Investigator, unless they are performed routinely as part of standard patient care.

Confirmation of the patient's consent and the informed consent process must be documented in the patient's medical notes. A copy of the signed consent form should be provided to the patient and the original retained in the site investigator file (SIF), which must be available for verification by ICR-CTSU study staff at any time.

Participants should be given the current ethics approved HALT patient information sheet for their consideration. Patients should only be asked to consent to the study after they have had sufficient time to consider the trial, and the opportunity to ask any further questions.

As part of the HALT trial, all patients will be asked to consent to the mandatory provision of research blood samples. In addition patients may be asked to consent to participate in the HALT translation sub-study involving the use of archival tissue where available and the provision of fresh tissue biopsies upon progression, where appropriate. Patients will also be asked to consent to participate in the HALT Quality of Life sub-study. Patients should be made aware that participation in the HALT translational sub-study or the quality of life sub-study is entirely voluntary. Refusal to participate in either sub-study will not result in ineligibility to participate in the main clinical trial and will not impact the medical care received. Further information regarding the HALT translational and quality of life sub-studies can be found in Section 19 of this document.

To facilitate linkage with routinely collected healthcare data patients will also be asked to consent to the collection of their full name, date of birth, hospital number, postcode and NHS number. Further details regarding the maintenance of confidentiality relating to the collection of these details can be found in Section 16.4 of this document.

7.3 Participation in other Clinical Trials

Patients who fulfil the HALT eligibility criteria will be given the opportunity to participate in the trial if they have participated in other clinical trials prior to recruitment. However, in instances where patients, having previously completed HALT participation by meeting the trial primary endpoint, go on to develop further oligoprogressive disease outside of the trial, these patients would not be considered eligible for re-entry into HALT. Participation in other clinical trials will be considered on a case by case basis by the Trial Management Group with due consideration given to the needs of the patient and impact on the conduct and outcome of both trials.

8 **REGISTRATION**

Once informed consent has been obtained, participants must be registered centrally with the trials unit (ICR-CTSU) before protocol required screening assessments commence.

Patients should be registered by emailing ICR-CTSU to request a call back on: [contact]:00-17:00 (UK time) Monday to Friday

The following information will be required at registration:

- Name of hospital, consultant and person registering patient
- Confirmation that the patient has given written informed consent for trial participation and for any sub-studies and the date consent obtained
- Patient's initials, hospital number and date of birth

The caller will be given the patient's unique registration number (Registration ID). Assessments of eligibility to be performed are detailed in section 10.1. Please note that CT scans/MRI scans/PET-CT scans performed as part of standard clinical practice, prior to registration, can be used if conducted ideally within 14 days, but at least within 1 month prior to registration. The patient scans must be uploaded as soon as possible after registration for review by the virtual MDT.

9 RANDOMISATION

Patients must be randomised centrally by the trials unit (ICR-CTSU) before trial treatment can commence.

Patients should be randomised by emailing ICR-CTSU to request a call back on: [contact] 09:00-17:00 (UK time) Monday to Friday

Randomisation should take place as soon after the date of consent as possible, once all eligibility assessments have been conducted and patient eligibility confirmed. Patients randomised to receive

SBRT should commence treatment within 4 weeks of randomisation. An eligibility and randomisation checklist must be completed prior to randomisation.

The following information will be required at randomisation:

- Name of hospital, patient's named consultant, name of SBRT planning clinician (if different from named consultant) to deliver SBRT to specific metastatic site and person randomising the patient
- Confirmation that patient is eligible for the trial by completion of the eligibility checklist
- Patient's full name, hospital number, date of birth, postcode and NHS/CHI number (or equivalent for international participants)
- EGFR vs other mutation (e.g. ALK, ROS-1 and MET)
- Number and location of extra-cranial OPD lesion(s)
- Tumour burden, classified as either 'high' or 'low' as evaluated by the virtual MDT (further details provided in Section 6)

The caller will be given the patient's unique randomisation number (Trial ID) and treatment allocation. Patients will be allocated to receive either SBRT and continuation of background TKI (SBRT treatment group) or continuation of background TKI alone (control group).

ICR-CTSU will email confirmation to the named contact(s) at the recruiting site to confirm a patients' entry into the trial.

Patients randomised to receive SBRT should commence treatment within 4 weeks of randomisation. Any delays encountered in commencing SBRT treatment should be notified to and discussed with the ICR-CTSU HALT trial team and the Chief Investigator

10 TRIAL ASSESSMENTS

All trial specific assessments must only be completed once the patient has provided informed consent for trial participation.

10.1 Screening Assessments

It is recommended that the following assessments are conducted within 30 days prior to randomisation unless otherwise indicated.

- CT scan/PET-CT scan confirming disease progression and current OPD (CT component of PET-CT should be of diagnostic quality). Baseline imaging modality should be used for subsequent follow-up imaging assessments. Scans conducted outside the trial can be used if performed ideally within 14 days, but at least within 1 month prior to registration; otherwise a repeat scan will be required to confirm eligibility. Central confirmation of OPD and suitability of all progressing lesions for SBRT will be performed by the HALT virtual MDT. Further details of this process can be found in Section 6.
- Complete medical history and physical examination
- Assessment of performance status (Karnofsky Index and ECOG)

HALT Protocol

- Local confirmation of diagnosis of advanced NSCLC with defined actionable mutation
- Evidence of confirmed radiological response to current TKI therapy (assessed locally usually within 2-3 months of commencing TKI therapy)
- Contrast enhanced CT or MRI brain scan to exclude new or progressing intracranial disease not suitable for surgery or SRS. If suitable scan was taken at the time of OPD confirmation a repeat scan is not necessary however this must be within 30 days prior to randomisation. Patients found to have new or progressing intracranial disease should be discussed at the local neuro-oncology MDT. If the intracranial disease is amenable to either surgery or SRS to the brain, the patient should have their intracranial disease treated accordingly and may enter the trial following this treatment provided they still meet the eligibility regarding their systemic disease. Having received treatment, patients may proceed to trial entry and commence trial treatment as indicated in the protocol (i.e. for patients randomised to the treatment group, SBRT should be delivered within 4 weeks of randomisation). Intracranial disease identified at trial entry not amenable to surgery or SRS is criteria for exclusion from the trial.
- Screening blood tests to assess suitability for SBRT depending on sites of OPD (please refer to HALT RT Planning and Delivery guidelines document for further details).
- Pregnancy test (if applicable)

The following assessments are required to confirm suitability for SBRT dependent on the location of OPD lesion(s) and confirm patient eligibility:

- Liver OPD lesions: INR and DMSA scan (or local equivalent for assessment of kidney function)
- Lung OPD lesions: Pulmonary function tests (FEV1, FVC and TLCO/KCO), baseline O₂ saturations, baseline, MRC dyspnoea score
- Adrenal OPD lesions: DMSA scan (or local equivalent for assessment of kidney function), baseline cortisol measurement

The following baseline assessments should be conducted once patient has been randomised:

- Baseline conditions
 - Patients randomised to both the control and treatment arms should have CTCAE assessments at baseline and at each subsequent follow up visit as indicated.
- Baseline quality of life questionnaire (completed prior to patient awareness of treatment allocation)
- Research blood sample collection
- Archival tumour block collection (if applicable)

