- For further details please refer to the HALT RT Planning and Delivery guidelines. Any assessments should be conducted <7 days prior to treatment
- ^j The baseline quality of life questionnaire should be completed after randomisation, prior to patient awareness of treatment allocation
- ^k Archival block or biopsy samples to be collected if patient has consented to donate tissue samples
- Anatomical sites imaged at point of enrolment should continue to be assessed at follow-up assessments (i.e. brain metastases)
- ^m Research blood samples will be collected from patients receiving SBRT after delivery of the first fraction. For all patients a sample should be collected upon progression
- ⁿ First 3 monthly visit only, not required thereafter

 Toxicity assessment required at first visit post disease progression and at 1 year after last dose of radiotherapy treatment (for SBRT arm only)

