12.2 Reporting Adverse Events to ICR-CTSU

For non-UK reporting requirements please see Appendix A7

Any toxicity, sign or symptom that occurs after randomisation which is not unequivocally due to progression of disease, should be considered an AE.

All AEs must be reported on the relevant electronic CRF and submitted to ICR-CTSU.

• Toxicity evaluation

The National Cancer Institute Common Terminology Criteria for Adverse Events (CTCAE) version 4 scoring criteria will be used for all toxicity assessments for patients randomised to both the treatment (SBRT) and control groups.

The severity of AEs should be graded according to the appropriate CTCAE criteria. For each AE, the highest grade observed since the last visit should be reported.

Whenever one or more toxicity/sign/symptom corresponds to a disease or a well-defined syndrome, only the main disease/syndrome should be reported.

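### Baseline CTCAE is graded after randomisation, once the site knows the arm, with no condition on awareness of allocation

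*Protocol*

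**What the plan says.** Protocol section 10.1 (Screening Assessments) ends with a list headed "The following baseline assessments should be conducted once patient has been randomised". It holds four items: baseline conditions, the baseline quality-of-life questionnaire, research blood, and the archival tumour block. Under baseline conditions it says: "Patients randomised to both the control and treatment arms should have CTCAE assessments at baseline", and then at each follow-up visit.

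Only the questionnaire carries a condition on who knows what. Section 10.1 wants it "completed prior to patient awareness of treatment allocation", and a footnote to the schedule in section 10.7 repeats that it "should be completed after randomisation, prior to patient awareness of treatment allocation". Section 20.2.3 also puts the first questionnaire before the patient learns the allocation.

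Other relevant places in the protocol:

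- **Section 9:** the person who telephones for randomisation is given the trial number and the arm in the same call.
- **Section 3:** the comparison is SBRT against no SBRT, and no sham or other blinding is described.
- **Section 4.2:** toxicity is graded with CTCAE v4.0, in clinician and, where available, patient versions.
- **Section 10.7, footnote b (Baseline column):** asks only that baseline follow confirmation of eligibility.
- **Section 13.3:** toxicity related to SBRT is summarised as frequencies and percentages at each time point. Proportions with any grade and with grade 3 or above are presented, and any comparison between arms uses Fisher's exact test.

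**The concern.** A baseline record separates what the patient brought into the trial from what arose in it. It does this best when nobody who completes it knows the arm. Here the record is made after the arm has been disclosed to the site, and nothing keeps the CTCAE rater, or a patient completing the patient version, unaware of it.

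The symptoms at issue are common ones. Patients enter with advanced lung cancer and are already on a TKI. Appendix A6 lists cough, dyspnoea, fatigue, nausea and diarrhoea among the expected events of SBRT, and any of these may plausibly be present at entry. A rater who knows that a patient is about to receive SBRT may list such symptoms more fully, or less fully, than for a control patient. If so, the same symptom at follow-up could be read as old in one arm and new in the other. The summaries of toxicity related to SBRT could then differ between arms partly because of how baseline was recorded.

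**Working it through.** There is no figure in the protocol to reproduce. The check sets the passages side by side.

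1. **Order of events.** Section 9: the call is made and the arm is disclosed to the caller. Section 10.1: baseline conditions and CTCAE follow randomisation. So the site holds the allocation before baseline CTCAE is graded.

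2. **Safeguards, item by item.** The questionnaire is patient-completed and protected by a condition on the patient's awareness in sections 10.1, 10.7 and 20.2.3. Clinician CTCAE has no such condition in any section. Neither does patient CTCAE.

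3. **Whether the timing is forced.** Footnote b of section 10.7 sets only a lower limit, confirmed eligibility. Section 9 requires eligibility to be confirmed before randomisation, so there is an interval between the two in which baseline could be recorded. Footnote b allows that interval and section 10.1 closes it. Medical history, physical examination, performance status and, for lung lesions, a dyspnoea score are already taken before randomisation, so adding CTCAE there is practicable.

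4. **Where the record could matter.** Section 13.3 counts toxicity related to SBRT. Whether a symptom was present at baseline bears on that attribution. Section 13.3 does not subtract baseline grades or model change from baseline, so attribution is the only route that the document supports.

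5. **How many are exposed.** All 110 planned patients (73 SBRT, 37 control; section 5.1) have baseline CTCAE under this rule. That is the number assessed, not the number whose record is altered. The protocol gives nothing from which to derive the latter.

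6. **Cost of moving it.** Section 13.1 plans 138 registrations for 110 randomisations, and 138 − 110 = 28. It attributes these to patients found ineligible. A baseline taken after eligibility is confirmed avoids forms for most of those 28.

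7. **Why not the whole screening window.** Screening may run from 30 days before randomisation, and SBRT should start within 4 weeks (28 days) after it. A baseline at the start of screening could precede SBRT by 30 + 28 = 58 days. A baseline taken just before the call precedes SBRT by little more than 28 days at most.

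**The case against.** The strongest reply is that little is at stake. All follow-up CTCAE grading is unblinded too, as SBRT against no SBRT makes hard to avoid, so baseline adds little to a bias already present. History, examination, performance status and, for lung lesions, dyspnoea score are recorded before randomisation and limit what can later be entered as pre-existing. Section 9 says that the caller learns the arm; it does not say who grades CTCAE. How baseline grades enter the analysis may be settled in the SAP, which is not shown.

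Most of this stands and keeps the point small. It does not remove it. Baseline is the one toxicity assessment that can be made free of the allocation at almost no cost, and the protocol already saw the need for this in the neighbouring item.

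Three stronger readings are tempting, and the document does not support them:

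- **That the quality-of-life baseline is compromised as well.** The patient completes the questionnaire, and three sections require this before the patient knows the arm. A patient told first would be a departure from the protocol, not a fault in it. All that remains is that no procedure for withholding the arm is described.
- **That a symptom recorded at this baseline is also an adverse event.** Section 12.2 covers "Any toxicity, sign or symptom that occurs after randomisation", and section 12.1 speaks of a detrimental change after randomisation. A symptom already present and merely written down later is neither.
- **That baseline grades are the reference for the planned toxicity comparison.** Section 13.3 states no such analysis.

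**Conclusion.** The point holds for baseline conditions and CTCAE only. Section 10.1 places them after disclosure of the arm to the site, without the condition that it gives the questionnaire, so what is recorded as pre-existing can depend on the arm. The possible consequence is confined to attribution and to the summaries of toxicity related to SBRT. PFS is untouched, and neither the size nor the direction of any bias can be derived from the protocol.

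This rests on two assumptions: that the trial is unblinded, which is inferred from the design because the protocol does not use the term, and that the arm given to the caller reaches whoever grades CTCAE. It is a cheap improvement, not an error that threatens a conclusion of the trial.

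**What to change.** In section 10.1, take baseline conditions and CTCAE (both versions) out of the post-randomisation list. Require them after eligibility is confirmed and before the randomisation call, as close to it as practicable and not anywhere in the 30-day screening window. This agrees with footnote b of section 10.7, which can stay as it is. Research blood and archival tissue can also stay where they are.

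The questionnaire's timing needs no correction. If it is convenient to complete it at the same visit, section 10.1 and the schedule footnote that places it after randomisation would need a matching change. Section 20.2.3 would not, because it already allows completion at any time after consent and before the patient knows the arm.

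The cost is a change of wording, a few baseline forms for eligible patients who are then not randomised, and a slightly longer interval between baseline and the start of SBRT.

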10.2 Pre-SBRT Treatment Assessments

Consideration should be given as to whether repeat organ function tests (as performed at screening) are required (e.g. blood tests, pulmonary function tests) as per OPD site, prior to each course of SBRT (initial, subsequent SBRT upon further oligoprogression) as detailed in the HALT RT Planning and Delivery guidelines document. A physical exam, including Karnofsky index and ECOG performance

assessment may also be required prior to delivery of repeat SBRT. Assessments should be conducted within 7 days prior to commencing SBRT treatment.

10.3 Post-treatment Follow-up

All patients will be assessed 8 weeks post randomisation and then subsequently at 3 monthly intervals (from 8 week assessment date) in line with routine care until disease progression is confirmed. The following assessments will be performed at each visit:

- Karnofsky Index and ECOG performance status
- Toxicity assessment including MRC dyspnoea score
- Post treatment QoL questionnaire (at 8 weeks post randomisation and first subsequent follow-up visit).
- Full blood count, urea, electrolytes and liver function tests (first 3 month visit only, not required thereafter)
- Tumour imaging assessment (imaging requirements at follow up visits will be determined by lesion location as identified at trial entry. The same imaging modality used at baseline should be used for subsequent follow-up assessments. Consideration should be given for repeat CT contrast/MRI brain as required)
- Current medication / treatment

Research blood samples will be taken at 8 weeks, 5 months and 8 months post-randomisation and upon progression (for patients randomised to receive SBRT an additional sample will be taken after delivery of the first fraction of SBRT).

Repeat SBRT – Only those patients allocated SBRT treatment at randomisation should be offered repeat SBRT treatment upon development of new OPD lesions or progression of existing extracranial lesions not progressing at trial entry, where the total number of progressing lesions at any one point remains ≤ 5 . Suitability of new OPD lesions for further SBRT will be based on the same criteria as at trial entry (visible, imaging defined targets suitable for SBRT, \leq 7cm). Where multiple lesions are treated over the course of the trial, composite dose volume data must be assessed and all normal tissue dose constraints need to be met by the composite plan. Particular caution is required where isodose lines overlap serial organs. Any previous radiotherapy before trial entry should also be taken into account. 50% isodose lines for plans to individual lesions should not overlap. A maximum of 5 thoracic lesions, 3 abdominal and 3 pelvic lesions can be considered for SBRT with composite planning confirming all normal tissue dose constraints are met.

Central confirmation of suitability may be provided following review of tumour imaging and/or planning scans by the virtual MDT if requested by the local research team. A period >3 months since the last SBRT treatment is required before commencing repeat SBRT. However, repeat SBRT can be considered within a shorter time interval if an early interval scan has been requested by the vMDT, or where the total number of OPD lesions to be treated remain \leq 5 and this has been agreed by the vMDT.

Re-irradiation – Further SBRT treatment of progressing OPD lesions previously treated with SBRT either as part of the trial or prior to trial entry is not permitted in the HALT trial. Assessment of progression in previously treated OPD lesions should be as defined in Section 4 Primary Endpoint.

Disease Progression - Upon confirmation of disease progression meeting the primary endpoint no further post-treatment follow up assessments are required. Patients should continue to attend routine clinic visits as per local practice and the procedure upon further disease progression detailed below should be followed.

If disease progression is suspected in the period between 3 monthly visits (>1 month prior to next scheduled visit) (i.e. development of clinical symptoms suggestive of disease progression) all post-treatment follow-up assessments as detailed above should be conducted. If progression is confirmed and no further SBRT is possible (control group/lesion not suitable to SBRT) patients should follow the procedure upon further disease progression (Section 10.4) from their next scheduled visit.

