10.4 Procedure upon further Disease Progression

All patients will continue background TKI treatment until a change in systemic therapy is indicated. This will be according to local clinical assessment and as per standard of care. Information regarding the local criteria used to determine a change in systemic treatment will be requested with details being provided by sites using the appropriate HALT eCRF.

Patient status will be reviewed at routine clinical visits until death. The following information should be recorded on the appropriate eCRF at each scheduled visit.

- Patient status
- Current treatment
- Assessment of toxicities required at first 3 month visit post disease progression and at 1 year after last dose of radiotherapy treatment (for SBRT arm only).

Upon confirmation of disease progression the following should be collected:

• Blood samples for ctDNA analysis

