13 STATISTICAL CONSIDERATIONS

13.1 Statistical Design and Sample Size Justification

HALT is a randomised, multi-centre, phase II/III study with planned international participation. The integrated phase II/III trial incorporates a transition to full phase III dependent on feasibility data obtained during the phase II trial. This design offers the most efficient use of time and resource compared to a standalone phase II trial followed by a separate phase III trial and allows maximum return of information in a relatively short timeframe. Progression to the phase III trial will be dependent on emerging feasibility data from the phase II trial including recruitment rates; safety and extent of opportunities for international participation (see section 11.5). With the development of novel actionable mutations and TKIs continuing to emerge both the phase II and III components of the study have proposed adaptive aspects to allow inclusion of additional patient groups with OPD on any other targeted treatments as they are introduced into routine practice.

Limited data is available on oligo-progression in patients with NSCLC, however a median time from radiological oligo-progression to widespread progression when continuing on a TKI alone (as per the control group) of approximately 3 months was estimated following a survey of U.K. oncologists and clinical members of the trial team. Furthermore, most oncologists surveyed considered 3 months to be a suitable level of additional benefit for the addition of SBRT (experimental treatment) to be considered a worthwhile intervention. Therefore median PFS for the SBRT group is assumed to be 6 months. Using these estimates together with a significance level of 5% (two-sided), 90% power, a 2:1 allocation ration (SBRT treatment:control), 110 randomised patients (anticipated 73:37) in total is required to obtain 97 PFS events. The sample size calculation uses the log rank test due to the possibility of non-proportional hazards.

The sample size calculation assumes a recruitment period of 36 months with a 6 monthly accrual percentage of total of 5%: 10%: 15%: 20%: 25%: 25% with a minimum of 6 months follow-up (total duration 42 months). It is assumed that the lost to follow up rate will be <1% due to the frequency of follow-ups in line with routine practice and the short expected median time to reaching the primary endpoint.

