20.2.3 Timing of data collection

Participants will be asked to complete the questionnaires after informed consent is obtained during their clinic visit at the following time points; 1) before treatment allocation is known to the patient (treatment vs control group)), 2) 8 weeks post randomisation and 3) during the first 3 monthly follow-up visit.

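### Quality-of-life forms stop at a primary-endpoint progression, so the 5-month summary by arm loses a larger share of control than SBRT patients by design

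*Protocol*

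**What the plan says.** Section 10.3 sets visits at 8 weeks after randomisation and every 3 months from then, "in line with routine care until disease progression is confirmed". The post-treatment questionnaire is one item on the list for those visits, due at 8 weeks and at the first 3-monthly visit, which the schedule table labels 5 months. The same section then states: "Upon confirmation of disease progression meeting the primary endpoint no further post-treatment follow up assessments are required".

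Section 10.4 lists what is recorded after progression: patient status, current treatment, a ctDNA blood sample and toxicity ("Assessment of toxicities required at first 3 month visit post disease progression"). It lists no questionnaire. The schedule table in 10.7 marks quality of life at baseline, 8 weeks and 5 months only, and leaves the disease-progression and post-progression columns empty for it.

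Section 20.2.3 places the last questionnaire "during the first 3 monthly follow-up visit" without a progression condition, and the trial schema does likewise. Neither provides a visit at which a progressed patient would complete it.

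Quality of life is a secondary endpoint (4.2). Section 13.3 presents it by treatment group at each time point, with longitudinal analysis as an option. Section 20.2.2 makes 8 weeks the primary time point.

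**The concern.** Whether a patient has a 5-month form depends on the trial's primary outcome. If SBRT delays progression as the design assumes, the two arms are thinned at different rates before that visit, and the groups summarised at 5 months are no longer the randomised groups. PFS events include symptomatic progression needing intervention (4.1), so the patients removed may well be those whose quality of life has fallen. Proportionally more of them would come from the control arm, which could hide a real benefit.

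This is a matter of data collection, so no later analysis plan can recover the forms. Section 20.2.4 names only uncompleted questionnaires and missed items as sources of missing data. The scoring-manual rules cited in 13.3 and 20.2.5 do not reach a form that was never scheduled.

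**Working it through.** **Inputs (section 13.1).** The control median PFS comes from a survey estimate of the time to "widespread progression when continuing on a TKI alone (as per the control group) of approximately 3 months". For the other arm: "Therefore median PFS for the SBRT group is assumed to be 6 months". The test uses a "significance level of 5% (two-sided), 90% power". Allocation is 2:1, with 73 SBRT and 37 control patients. Exponential PFS is my assumption; it makes the hazard ratio 3/6 = 0.5.

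**Reproducing the plan's own figure.**
- Schoenfeld events: (1.960 + 1.282)² / [(1/3)(2/3)(ln 0.5)²] = 98.4, so 99 (98 with an allocation of 37/110). The protocol states 97; power at 97 events is 0.896.
- With the stated staggered accrual and 42 months in total, the event probabilities are 0.956 (control) and 0.837 (SBRT). Expected events are 37 × 0.956 + 73 × 0.837 = 96.5.
- The exponential model with these medians therefore matches the design closely.

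**Share with a PFS event by time t:** 1 − 2^(−t/median). Eight weeks is 56/30.4375 = 1.84 months; the 5-month visit is 1.84 + 3 = 4.84 months.

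| Which events remove the 5-month form | t (months) | Control | SBRT |
|---|---|---|---|
| Only those found by the 8-week scan (lowest) | 1.84 | 34.6% (12.8 of 37) | 19.1% (14.0 of 73) |
| All except those in the last month, found at the visit itself | 3.84 | 58.8% (21.8) | 35.8% (26.2) |
| All, each found as it occurs (upper bound) | 4.84 | 67.3% (24.9) | 42.8% (31.3) |

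The control share is 1.6 to 1.8 times the SBRT share throughout. Because of 2:1 allocation, the head counts are similar or higher in the SBRT arm.

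**Taking out deaths.** Death is a PFS event and cannot yield a form. Sections 13.1 and A1 give, for phase III planning, a median survival of 12 months in controls and 15 to 18 months with SBRT. Assuming exponential survival, the share dead at 4.84 months is:
- control: 1 − 2^(−4.84/12) = 24.4% (9.0 of 37);
- SBRT: 1 − 2^(−4.84/15) = 20.0% (14.6 of 73), or 1 − 2^(−4.84/18) = 17.0% (12.4 of 73).

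Every death is also a PFS event, so alive and progressed is the difference:
- control: 67.3 − 24.4 = 42.9%, about 16 of 37;
- SBRT: 42.8 − 20.0 = 22.8% to 42.8 − 17.0 = 25.8%, about 17 to 19 of 73.

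At the upper bound, about 33 to 35 forms are recoverable.

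**Sensitivity to the PFS effect (upper bound, 4.84 months).** Medians of 4 and 6 months give 56.8% vs 42.8%; 3 and 4 months give 67.3% vs 56.8%; equal medians of 3 months give 67.3% in both arms and no gap.

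**The case against.** The strongest reply is that little rests on 5 months. Section 20.2.2 makes 8 weeks the primary time point. Section 20.2.5 describes patient-reported outcomes as a supplement to clinician-assessed toxicity, without a sample size calculation. Section 13.3 promises descriptive statistics and only permits longitudinal modelling. Scores after progression may also reflect next-line therapy, so stopping at progression is a choice one can defend. This limits the weight of the point. It does not make the 5-month figures, which 13.3 will still present by arm, a comparison of the randomised groups.

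Some forms may also survive. A patient whose progression is first seen on the 5-month scan attends that visit and can complete the form. Section 10.3 asks for all follow-up assessments when progression is suspected more than a month before a scheduled visit, so some patients may give an off-schedule form then. The quality-of-life study is voluntary (7.2, 20.2.2), so the denominators of 37 and 73 are maxima. All of this stands, and is why the largest figures are stated as upper bounds.

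Three stronger readings are not supported:
- A reader might infer that more control than SBRT patients are missing in number. The head counts do not run that way; only the proportions do.
- A reader might infer that the 8-week result is equally compromised. At most 35% vs 19% have an event by then, and no scan is scheduled earlier, so most such events would be found at the visit where the form is due.
- Section 10.3 could be read as taking control patients off the schedule at any confirmed progression between visits, since it cites the control group as a case where further SBRT is not possible. The preceding paragraph ties the end of assessments to the primary endpoint. The two paragraphs should be reconciled, but the figures here do not rely on the wider reading.

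**Conclusion.** The point holds for the 5-month and any longitudinal comparison of a secondary endpoint. By design, the 5-month summary excludes patients already confirmed to have reached the primary endpoint, and a larger share of control than SBRT patients is lost: between 35% vs 19% and 67% vs 43%, deaths included. Among patients alive and progressed, the upper bound is about 43% vs 23-26%, a gap of roughly 17 to 20 points.

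These sizes rest on exponential PFS and survival, on the protocol's planning medians, and on full consent to the quality-of-life study. The gap shrinks with a smaller PFS effect and disappears with none, so it is widest when SBRT works. The direction of any resulting bias is plausible but cannot be shown from the protocol.

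**What to change.** In sections 10.3, 10.4 and 20.2.3 and the schedule table, state that the 8-week and 5-month questionnaires are collected at those times from randomisation, in both arms, in every living patient who consented to the quality-of-life study, regardless of progression. Use the nearest routine clinic visit; section 10.4 already has patients reviewed at routine visits until death. Do not tie the form to the post-progression toxicity visit, which is timed from progression and, as worded, may apply to the SBRT arm only.

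The cost is a small amendment and up to about 35 extra questionnaire sets, fewer if some patients decline the quality-of-life study. Some later scores will partly reflect next-line therapy, which the report should say.
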